## Progression of interventions to phase two.

In phase one, we will be evaluating various potential outcome measures for phase two whilst also ascertaining acceptability and feasibility of the three interventions to progress to phase 2. Phase two will be assessing the effectiveness of any interventions that progress to phase 2. Further selection criteria are explained below.

Interventions will only progress to phase two (effectiveness trial) if there is a high degree of acceptability and feasibility demonstrated in phase 1. Thresholds for progression to phase two are:

- 1. Green: Progress to phase 2 if >75% of phase 1 participants are satisfied/ very satisfied with the support and engaged with the support.
- 2. Amber: Consider progression to phase 2 with study team, charity, and patient group discussion, and if intervention acceptability and engagement can be feasibly improved, if between 50-75% of participants are satisfied and engaged with the support.
- 3. Red: Do not progress any intervention where <50% of participants are satisfied and engaged.

In addition, interventions that are found to not be feasible for the providers or the research team to progress to larger numbers in phase 2 will be excluded. Interventions may be trialled together for comparison or may be separate trials with separate control groups for phase two depending on phase one findings.

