#### 6.5 Participant withdrawal

Participants may be withdrawn from the intervention groups and/or the whole study either at their own request, at the request of the intervention provider or at the discretion of the investigator. Participants will be made aware from the information sheet and in the allocation of group letter of how to withdraw and that it will not affect their medical care. Participants will be given the contact details of research staff and informed of how to report unacceptable or unkind behaviour within their intervention group. Participants whose behaviour is not acceptable or unkind will be initially warned for more minor issues and/or withdrawn from the group by study staff.

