We will also assess the association between pre-defined pairs of variables of interest ) using Pearson correlation coefficient with Chi- Square test. T-tests, Wilcoxon-Mann Whitney tests, Chi-Square tests, Kruskal Wallis tests and one-way/factorial ANOVA will be used appropriately to compare the mean scores, frequencies and impact between groups of patients. Regression models will be used to assess the effect of multiple variables on specific outcomes. As this is a very unexplored area, some additional exploratory analysis will occur in addition to pre-specified measures in order to identify priorities for future research.

Prior to the main analysis, we will conduct data cleaning. Percentages of invalid values, outliers and missing data will be reported. We will also investigate any patterns of missing data. Where appropriate, theoretical and/or clinical criteria will be used to identify invalid values or outliers. Depending on their type and prevalence we will decide on the most appropriate way of addressing. Our options include data exclusion from the rest of the analysis, data replacement with mean or mode values, or data inclusion as separate category (in case of missing data). Our primary option is to conduct "complete-case" analyses. We will not use multiple imputation for missing data. In case of highly prevalent missing data (more than 10% of the sample), sensitivities analyses based on the other option of missing data addressing will be used to assess the robustness of our findings.

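### For continuous outcome scores, the planned check on missing data comes down to mean replacement, which cannot test robustness, and multiple imputation is ruled out

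*Protocol*

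**What the plan says.** All the missing-data rules are in the protocol, section 6.7 Analysis and outcome measures, quantitative part.

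- Primary method: "Our primary option is to conduct 'complete-case' analyses".
- Listed ways of handling invalid values, outliers and missing data: "Our options include data exclusion from the rest of the analysis, data replacement with mean or mode values". A third way is listed for missing values alone, which may be kept as a category of their own. The choice is to depend on the type and prevalence of the problem. The text does not say whether the mean is that of the arm or of the whole sample.
- Exclusion of a method: "We will not use multiple imputation for missing data".
- Robustness: "In case of highly prevalent missing data (more than 10% of the sample), sensitivities analyses based on the other option of missing data addressing" are to be run.
- Outliers: "theoretical and/or clinical criteria will be used to identify invalid values or outliers". No cut-off is given.

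Two other places bear on the point. Section 6.1 sets the progression rule: "Green: Progress to phase 2 if >75% of phase 1 participants are satisfied/ very satisfied with the support and engaged with the support"; amber is 50–75%. It does not say how a participant without satisfaction or engagement data is counted. Section 6.5 allows withdrawal from the intervention group or the whole study at the participant's own wish, or "at the request of the intervention provider or at the discretion of the investigator".

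**The concern.** A sensitivity analysis for missing data should show whether the conclusion survives if the people who did not answer differ from those who did. The plan names its alternatives, and none of them does this for a continuous outcome. The GAD-7, PHQ-8, FACIT-F, loneliness, resilience and ADAPT scores cannot take a separate missing category unless they are first cut into bands. Once exclusion is the primary method and multiple imputation is barred, mean replacement is what remains.

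The interventions are remote and evident to participants, follow-up is by electronic questionnaire with up to three email reminders (section 6.6), and a request from an intervention provider can remove people only from an intervention arm. Loss that differs by arm is therefore plausible, although the protocol gives no expected rate. The results feed forward: phase 1 change scores help to choose phase 2 outcomes, phase 1 effect estimates inform phase 2 sample sizes, and the same analysis section governs the phase 2 effectiveness comparison.

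**Working it through.** **Inputs.** From the protocol: 30 per arm and 120 in total in phase 1 (section 4), the 10% trigger (section 6.7) and the 75% and 50% thresholds (section 6.1). Assumed, because the protocol gives no drop-out rate, effect size or standard deviation: missing fraction m of 10%, 20% or 30%, equal in two arms and completely at random; SD 1; true effect 0 or 0.50 SD; unadjusted two-sided 5% t-test. The plan has no figure of its own to reproduce on this point.

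**Arm-mean replacement.** Filled values add nothing to the residual sum of squares but are counted as observations.
- True SE = √(2/[n(1 − m)]).
- Reported SE ≈ √(2(1 − m)/n).
- Ratio = 1 − m.
- Type I error ≈ 2[1 − Φ(1.96(1 − m))], which is 7.8%, 11.7% and 17.0% at 10%, 20% and 30% missing.

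**Overall-mean replacement.** Each arm mean is pulled toward the common mean, so the estimated difference is (1 − m) × the true difference: 0.50 becomes 0.45, 0.40 and 0.35.

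Simulation with 40,000 replicates and 30 per arm agrees:

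| m | True SE | SE reported, arm mean | Type I, complete-case | Type I, arm mean | Effect 0.50, complete-case | Effect 0.50, overall mean |
|---|---|---|---|---|---|---|
| 10% | 0.272 | 0.243 | 4.9% | 7.6% | 0.50 | 0.45 |
| 20% | 0.289 | 0.229 | 5.2% | 11.9% | 0.50 | 0.40 |
| 30% | 0.307 | 0.213 | 4.8% | 17.1% | 0.50 | 0.35 |

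With 100 per arm, arm-mean fill gave type I errors of 7.8%, 11.7% and 17.1%, so a larger phase 2 does not cure it.

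Neither fill brings in new information. Arm-mean fill returns the complete-case estimate with too small an SE. Overall-mean fill shrinks estimate and SE together and returns almost the same test: power for a 0.50 effect was 43.6%, 39.7% and 35.1%, against 43.6%, 39.6% and 35.0% for complete cases.

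**Selection bias in the complete-case analysis (assumed sizes).** If 20% are lost in one arm only, and loss has latent correlation ρ with the outcome, the bias is ρ × 0.28/0.80 SD. That is 0.105 SD at ρ = 0.3 and 0.175 SD at ρ = 0.5. It is zero if the same loss and mechanism apply in both arms.

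**Trigger.** If the sample is all 120, losing 12 of the 30 in one arm (40%) is 12/120 = 10%, which is not more than 10%, so no sensitivity analysis follows. Read per arm, 3/30 = 10% does not trigger it either.

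**Progression denominator (30 allocated).**
- One missing: 22/30 = 73.3% (amber); responders only 22/29 = 75.9% (green); mode-filled 23/30 = 76.7% (green).
- Three missing: 21/30 = 70.0% (amber); responders only 21/27 = 77.8% (green); mode-filled 24/30 = 80.0% (green).
- At a true rate of 70%, the chance of green is 0.28 with full data. With 10% missing at random it is 0.26 on responders and 0.41 mode-filled. If all the missing are dissatisfied it is 0.61 on responders.
- With all 30 as denominator and the missing counted as not satisfied, green needs 23/30 (76.7%) however many are missing.

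**The case against.** The strongest reply is that the primary analysis is not at fault. Complete-case analysis kept type I error at 4.8–5.2% and the effect at 0.50 under random loss. The faults in standard errors and effect size belong to mean replacement, which stands behind it as an alternative or check. This stands: a reader who infers that the main results will have wrong standard errors goes further than the plan supports.

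Five further readings are tempting and are not supported.

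- *Mean or mode replacement is the only back-up.* A separate missing category is also listed. For the categorical satisfaction item it would leave non-responders in the denominator and the result amber. The complaint is confined to continuous scores.
- *Non-response will turn amber into green.* Section 6.1 speaks of participants, and nothing applies the complete-case rule to it. If participants means everyone allocated, no shift occurs. The usage is not settled, however: section 6.7 on outcome selection sets one 25% limit on participants and another, for FACIT-F, on respondents. Under random loss, responders-only counting does not raise the chance of green. An illustration with 8 of 30 silent, 17/22 = 77% against 17/30 = 57%, assumes that all eight are dissatisfied or disengaged. Amber also permits progression after discussion.
- *Severely affected patients will be deleted as outliers.* The text does not say that valid in-range scores will be removed. Excluding values beyond 2 or 2.5 SD within arm would raise type I error to about 9.7% or 6.8%, but those cut-offs are not the protocol's.
- *The selection bias is 0.10–0.18 SD.* This rests on an assumed 20% loss in one arm only, and the planned regression on other variables might reduce it.
- *Withdrawn participants' data will be discarded.* Section 6.5 does not say so.

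It can also be said that estimation detail belongs in a statistical analysis plan. That would excuse silence. Here the protocol itself names mean replacement and prohibits multiple imputation.

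**Conclusion.** The concern holds in a limited form. For continuous outcomes, the robustness check that the protocol prescribes gives either a standard error too small by the missing fraction or an effect shrunken by it, and in neither case tests whether non-responders differ. The (1 − m) factors follow from the method; the percentages assume random loss, equal in the two arms, and an unadjusted comparison. The ban on multiple imputation removes the obvious replacement, and the 10% trigger can leave 40% loss in one arm unexamined if it is read across all 120.

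Complete-case analysis as primary is a risk, not an error: its bias depends on loss that differs by arm and relates to outcome, which the protocol does not quantify. The progression denominator and the outlier rule need clarifying; neither is a demonstrated mistake. This should be fixed. Phase 2 outcomes and sample sizes are still open, so there is room to do it.

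**What to change.** In section 6.7 (Analysis and outcome measures):

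- Delete mean and mode replacement for outcomes, and the statement ruling out multiple imputation.
- Make the primary analysis a baseline-adjusted linear mixed model of both follow-ups, by randomised arm, using everyone with at least one follow-up.
- Add multiple imputation with delta shifts by arm as the sensitivity analysis, at any level of missingness. This also brings in people with no follow-up, whom the mixed model leaves out.
- State that only impossible values are excluded and that in-range scores are kept.

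In section 6.1, state that the progression denominator is all participants allocated to the arm, with non-responders counted as not satisfied or engaged.

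The cost is wording and modest extra analysis. Against a responders-only count, each progression percentage is multiplied by the response rate: 22/29 = 75.9% becomes 22/30 = 73.3%. With heavy non-response the fall would be large.

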## **Advisory Group:**

[name], Birmingham (Iupus specialist)

[name] – Patient member

[name], Addenbrookes (Vasculitis and nephritis consultant)

[name]-Patient member

The study will be based at the Primary Care Unit, Department of Public Health & Primary Care, Institute of Public Health, University [name]. The team will hold monthly meetings to review ongoing progress of the study and any amendments required. The team will include patient and clinician advisors. An advisory board led by [name] (Addenbrookes) and containing two patient representatives will meet with the study team a minimum of 3 times including: prior to the interventions commencing, during the intervention period, and on deciding which interventions to proceed to phase 2. They will meet on additional occasions should any difficulties arise at any stage.

The Principal Investigators have overall responsibility for the study and shall oversee all study management.

## 7.2 Study Funding

The research costs for the study are funded by LUPUS UK and The Lupus Trust.

#### 7.4 Insurance/Indemnity

The University of Cambridge as research sponsor indemnifies its staff, research participants and research protocols with public liability insurance and clinical trials insurance.

## 7.5 Adverse Incident reporting

As this study is not a 'clinical trial of an investigational medicinal product (CTIMP)' it does not fall under The Medicines for Human Use (Clinical Trials) Regulations 2004 (as amended).

The research team will not collect data on adverse events (AEs), serious adverse events (SAEs) or suspected unexpected serious adverse reactions (SUSARs) as defined by these regulations. However, even in non-pharmaceutical research, such as this study, adverse incidents may still happen, for example:

- breach of confidentiality
- patient complains about any aspect of study
- deviation from study protocol (e.g. recruiting before consent)
- equipment failure
- aggressive/ unacceptable behaviour of a participant towards the support group, researcher, staff or others.
- Responses highlight serious concern of risk to a patient

Concerns of risk to a participant will be immediately reported to the relevant authorities and the Chief Investigator. Unacceptable behaviour within support groups will result in expulsion of that participant from the group. Adverse incidents relating to the conduct of this research must be reported to the Chief Investigator within 5 working days of any team member becoming aware of the incident.

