#### 3. Physical activity course

This will be provided by a trained Pilates instructor (Flexifit Pilates) via Zoom. Participants will receive the intervention in groups of 15, twice a week, in 50-minute sessions over 8 weeks via Zoom. Exercises will be tailored to Ppts with chronic diseases with the emphasis on participation, social interaction and enjoyment.

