## 6. The 'ADAPT' study

6.1 Study aims, objectives and progression

#### Aim

To assess the acceptability, feasibility and effectiveness of methods of remote psychosocial support for SARDs patients. For the interventions trialled (if effective and acceptable) to be incorporated as an adjunct to usual care.

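### Section 7.5 puts an incident process in place of adverse event collection, so injuries, flares and similar events cannot be estimated or compared by arm

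*Protocol*

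**What the plan says.** Protocol section 7.5 gives its reason first: "As this study is not a 'clinical trial of an investigational medicinal product (CTIMP)' it does not fall under" the 2004 medicines regulations. It then states that "The research team will not collect data on adverse events (AEs), serious adverse events (SAEs) or suspected unexpected serious adverse reactions (SUSARs", and the sentence closes with a qualifier that matters: "suspected unexpected serious adverse reactions (SUSARs) as defined by these regulations".

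The section next sets up reporting of adverse incidents and gives six examples. Five concern conduct or process: a confidentiality breach, a complaint, a protocol deviation, equipment failure and unacceptable behaviour. The sixth is that "Responses highlight serious concern of risk to a patient". Concerns of that kind go at once to the authorities and the Chief Investigator. For the rest, "Adverse incidents relating to the conduct of this research must be reported to the Chief Investigator within 5 working days" of a team member becoming aware of them.

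Two decisions depend on the results. Section 6.1 sets the progression rule, whose top level reads: "Green: Progress to phase 2 if >75% of phase 1 participants are satisfied/ very satisfied with the support and engaged with the support". The amber and red levels use the same two quantities, and a feasibility condition is added. The aim, also in section 6.1, is "For the interventions trialled (if effective and acceptable) to be incorporated as an adjunct to usual care". Neither text mentions harm.

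The interventions include a Pilates course (synopsis, item 3): "Participants will receive the intervention in groups of 15, twice a week, in 50-minute sessions over 8 weeks via Zoom". They also include fortnightly one-to-one listening sessions over 12 weeks, and a text programme with optional WhatsApp groups that the researcher sets up and then leaves.

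**The concern.** Being outside the medicines regulations removes a statutory reporting duty. It does not answer whether an exercise course, talking sessions or peer groups have unwanted effects, and no other reason for leaving events uncollected is given.

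The incident process does not fill the gap. It depends on a team member becoming aware of something. Participants in the exercise and listening arms meet an instructor or listener regularly, while no such contact is described for controls. Spontaneous reports would therefore arise at different rates for reasons unrelated to risk, and a count by arm could not be read as a comparison.

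At stake is the basis for two decisions: which interventions go forward after phase 1, and which are offered alongside usual care. Both would be taken on satisfaction, engagement, feasibility and benefit, with no structured count of untoward events to set against them. A statistical analysis plan could not repair this later, because it cannot analyse events that were never asked about.

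**Working it through.** **1. The plan's own figures.** The protocol gives no figure on harms. The arm sizes in the synopsis add up: phase 1, 4 × 30 = 120; phase 2 (provisional), 100 exercise + 100 listening + 300 text + 300 control = 800.

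**2. What each planned data source could show.**

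| Source (protocol section) | Could show | Could not show |
|---|---|---|
| Adverse incidents (7.5) | Complaints; serious risk evident from a response | A rate by arm: nobody is asked, and no denominator or comparison is stated |
| PHQ-8, GAD-7, FACIT-F, EQ-5D-5L, loneliness (6.6) | A shift in depression, anxiety, fatigue, quality of life or loneliness against control | Injury; discrete events |
| Pain, fatigue, cognition, self-rated disease activity (6.6) | A shift in self-rated symptoms or activity | Flare as a counted event; injury |
| Health service contacts (6.6, Economic analysis) | Emergency visits and admitted stays, if kept in the final list | Anything in phase 1, where cost work is qualitative |
| Interviews and open survey answers (6.6) | Individual accounts | A comparison across arms |

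No row gives a count of injuries, flares or session-related distress that is asked in the same way of every arm. The service-use row comes too late for the phase 1 progression decision.

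**3. What identical questions would give if no events were reported.** The exact one-sided 95% upper limit is 1 − 0.05^(1/n).

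- n = 30: 1 − 0.05^(1/30) = 0.095, or 9.5%
- n = 100: 1 − 0.05^(1/100) = 0.030, or 3.0%
- n = 300: 1 − 0.05^(1/300) = 0.010, or 1.0%

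**4. Chance of seeing at least one event.** This is 1 − (1 − p)^n. With an assumed true risk of p = 2%:

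- n = 30: 1 − 0.98^30 = 46% (0.455)
- n = 100: 1 − 0.98^100 = 87%
- n = 300: 1 − 0.98^300 = 99.8%

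**5. Power to compare arms.** Normal approximation, two-sided 5%: power = Φ[(|p1 − p0| − 1.96 × SE0) / SE1], with SE0 from the pooled rate and SE1 from the separate rates. The protocol gives no event rates, so the pairs below are assumptions.

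| Control v intervention | Phase 1, 30 v 30 | Phase 2, 300 control v 100 |
|---|---|---|
| 2% v 10% | 25% | 87% |
| 5% v 15% | 25% | 86% |
| 5% v 10% | 11% | 44% |

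Example, 2% v 10% at 30 v 30: SE0 = √(2 × 0.06 × 0.94 / 30) = 0.0613; SE1 = √((0.02 × 0.98 + 0.10 × 0.90) / 30) = 0.0604; (0.08 − 1.96 × 0.0613) / 0.0604 = −0.66, and Φ(−0.66) = 25%. The expected counts here are only 0.6 and 3, so the approximation is rough. Phase 1 counts can describe but not test; phase 2 could detect large differences.

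**The case against.** A reader might infer that the plan cannot say whether the interventions do harm. The protocol does not support that. It collects depression, anxiety, fatigue, quality of life, loneliness, pain and self-rated disease activity, follows participants at 12 weeks and 6 months, has a randomised control, and plans to test differences between groups. An average worsening from talking sessions or peer contact would appear as a negative effect.

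Three related readings also go too far.

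- That all harm information is ruled out: the exclusion is tied to the regulatory definitions, and an injury or upset could enter as a complaint or a risk concern.
- That scores are looked at only as averages: section 6.7 (Analysis and outcome measures) plans medians, ranges, boxplots and within-person change, so individual deterioration can be derived.
- That nothing would be seen in either phase: phase 2 is to record service contacts, likely to include emergency visits and admissions.

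It is also fair that the exercise is described as gentle and tailored to chronic disease, that section 5 cites a study in which exercise did not worsen lupus activity, that the choice is stated openly in an ethics-reviewed study, and that interviews and the advisory group could bring problems to the progression discussion. Formal comparison in phase 1 would be weak in any case.

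All of this narrows the point without removing it. No listed scale records an injury. A mean can improve while a few people get worse. The primary approach is complete-case without multiple imputation, so people who leave because of harm may drop out of the comparison, and section 6.5 does not mention recording why they left. The cited exercise study shows that the question is thought relevant, but phase 2 admits any systemic autoimmune rheumatic disease, not lupus alone.

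**Conclusion.** The point holds in a limited form. The protocol has no systematic collection, identical across arms, of untoward events such as injury, flare or session-related distress, and neither progression nor adoption refers to harm. Event-type harms therefore cannot be estimated or compared by arm. Questionnaire worsening can be, and phase 2 service use may reveal some serious events.

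This is a weakness in a stated choice, not a contradiction or a miscalculation, and it should be changed because the remedy is cheap. What is lost is a bound of about 9.5% per arm in phase 1. In phase 2 it is about 3.0% for exercise and listening and 1.0% for text, if no events occur, if the provisional sizes are kept and if everyone answers. The bounds need no assumed event rate. The detection and power figures rest on assumed rates and serve only as illustration.

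**What to change.** In section 7.5, keep the statement that the reporting duties for medicine trials do not apply, and add that untoward events will be asked about.

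- **Questions.** Put two or three identical items in follow-ups 1 and 2 for every arm, control included, with the same recall period: any new injury; any self-reported flare or urgent care contact; any worsening of mental health that needed help. In phase 2, take urgent care from the planned service-use items so that it is not asked twice.
- **Table.** Report counts and denominators by arm, with the share who worsen on PHQ-8 and on GAD-7 by an amount fixed before the data are seen.
- **Use.** Add a line to section 6.1 that the phase 1 table goes to the meeting that decides progression, as descriptive information and not as a test.

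The cost is two or three survey items, one table and slightly more burden on respondents. The limitation to state alongside it is that phase 1 counts are imprecise: none in 30 is still compatible with a risk of up to 9.5%.
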